For Phase 2 of the study, we will enroll 30 participants (15 from each of our clinical sites)

Study Design

In Phase 1 we will use a qualitative descriptive design, convening interviews/focus groups with stakeholders to guide the development of *MAP*. During this phase we will finalize the intervention protocol and develop promotional and training materials.

In Phase 2, we will evaluate the preliminary efficacy and feasibility of *MAP* using a pre-post design.

Study Duration

The study will last for two years. We anticipate completing Phase 1 in the first year. Participants of Phase 1 of the study will participate in one focus group or interview that will last about 1.5 hours.

We have completed Phase 1 of the study. We anticipate completing Phase 2 in the second year of the study. Participants of Phase 2 of the study will participate in a multi-level intervention that will last for 6 months.

Outcome Variables

In Phase 1, there are no outcome variables.

In Phase 2, our primary outcomes include portal use (e.g., number of logins) and glycosylated hemoglobin (A1C) measured with a fingerstick of blood and analyzed with the A1CNow+ system. Secondary outcomes include: patient portal engagement (number of clinic appointments, use of community resources, medication refills, ER visits, and hospitalizations during the previous 3 months). Other secondary outcomes include T2D clinical management (EMR data of A1C, blood pressure, lipid profile, BMI), self-management (medication, blood glucose monitoring, healthy eating, physical activity), psychosocial outcomes (diabetes self-efficacy, autonomy support, diabetes distress) technology acceptance/use/confidence, and satisfaction.

We will also collect data on the intervention implementation which will be assessed by data on the sequence and timing of sessions, # of rescheduled/reminders for sessions, and how the portal was used by patients, CHWs, nurses, and providers. Implementation will also be measured via treatment fidelity. Lastly, we will use field notes and meeting notes from training and communication with interventionists to determine barriers and facilitators to program implementation.

Locations/Facilities

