In Phase 2, we will use a pre-post design, collecting data from participants at baseline, 3 and 6 months. We will evaluate change over time in participants.

Study Design:

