4.2.2 Secondary and Exploratory Outcome Variables/Endpoints (if applicable)

In Phase 1, this is not applicable.

In Phase 2, secondary outcomes include: a) patient engagement with care (clinic appointments, referrals, ER visits, hospitalizations, use of community resources for social determinants of health); b) T2D clinical management (EMR data of A1C, blood pressure, lipid profile, BMI); c) T2D self-management (medication, blood glucose monitoring, healthy eating, physical activity); d) psychosocial outcomes (diabetes self-efficacy, autonomy support, and diabetes distress); e) technology outcomes (digital literacy, acceptance/use/confidence); and f) satisfaction.

We will also collect data on the intervention implementation which will be assessed by data on the sequence and timing of sessions, # of rescheduled/reminders for sessions, and how the portal was used by patients, CHWs, nurses, and providers. Implementation will also be measured via treatment fidelity. Lastly, we will use data from all field notes of trainings and meetings with interventionists to determine barriers and facilitators to implementation.

5 Study Participants

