5.2 Number of Participants

For Phase 1, we will recruit health care providers (n=5), CHWs, (n=2), and adults with T2D (n=5), at each clinical site (total sample: 10 providers, 4 CHWs, and 10 adults with T2D).

For Phase 2, we will recruit 30 adults with T2D (n=15 from each clinic).

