7.1 Sample Size Considerations

Phase 1: Not applicable

Phase 2: Since this is a pilot study to provide preliminary data for a future large study, we conducted a power analysis to show an effect size on A1C using a feasible sample size of 30 participants. We chose the more conservative approach to power on A1C vs. portal logins as we anticipate a smaller effect size on A1C. In our recent study with low-income Latinx adults, we obtained a standard deviation of 1.2 and a sample correlation of 0.57 in repeatedly measured A1C over 6 months. The estimated standard deviation of changed A1C will be 0.72 and the sample size of 30 will produce a standard error of 0.13. Therefore, the proposed sample size of 30 could estimate a change of A1C over time with a margin of $\pm 0.27\%$ A1C for 95% confidence interval.

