7.2 Planned Analyses

Phase 1 analysis:

The sample of participants in the interviews/focus groups will be described using frequency distributions and appropriate summary statistics (SAS version 9.4). Content analysis will be used to analyze qualitative data from each type of stakeholder along with field notes and interviewer observations (Hsieh, 2005) Rigor for this process includes: (a) transcribing taped interviews; (b) checking transcripts against tapes for accuracy; (c) developing coding categories by two members of the research team; (d) assigning codes of text with appropriate checks; (e) reviewing coded data to identify themes across participants; and (f) a team approach to data analysis. At research team meetings we will assess researcher bias, coding saturation, and interpretative congruence. Results will be used to finalize the intervention protocol for implementation in Phase 2

Phase 2 Analysis: Data will be collected in the form of questionnaires online on the secure REDCap system. A1C data, electronic medical record data and patient portal data will be entered into REDCap or Excel and merged into one database. All data that are downloaded from REDCap or Excel will be onto a Yale server, which has several secure firewall systems. Descriptive analyses will be performed to assess demographic and clinical characteristics of the sample. Feasibility data will be summarized. Distributions of outcome variables will be examined for central tendency and dispersion. We will estimate the Cohen's D effect size of MAP on A1C and will examine the intervention effect over 6 months using generalized linear mixed model (GLMM) with random intercept, which will incorporate the correlation within repeatedly measured A1C. The slope of time will represent the average change of A1C over 6 months. The GLMM will include all participants with data at baseline and at least one of post-intervention value and will handle missing data using maximum likelihood approach. To confirm findings with missing data, we will rerun the GLMM with multiple imputations which will be produced by assuming multivariate normal distribution of repeatedly measured A1C. Number of logins and the repeatedly measured secondary outcomes will be analyzed with the same approach using the GLMM. Residuals will be assessed for normality assumption and

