variables will be transformed with an appropriate form when the normality assumption does not hold. Count data such as portal use, clinic appointments, ER visits, and hospitalizations will be modeled using Poisson or Negative Binomial regression model. For exceeding zero count (i.e. a high proportion of no appointment, ER visit, hospitalization), zero-inflated regression models will be employed. We will also estimate the effects of portal use (frequency, type) and feasibility factors (e.g., acceptability, attendance, fidelity) on A1c at 6 months after controlling for baseline A1c using generalized linear model (GLM). For future research with a large sample size, we will obtain an effect size (partial eta square) of each factor from GLM. Qualitative data will be analyzed using the aforementioned content analysis approach.

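### The switch to zero-inflated models is triggered by many zeros, which rare events produce anyway, and the plan does not name the effect it would then report

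*Combined protocol and SAP*

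**What the plan says.** Section 7.2 sets the base model: "Count data such as portal use, clinic appointments, ER visits, and hospitalizations will be modeled using Poisson or Negative Binomial regression model". It then gives a rule for changing it: "For exceeding zero count (i.e. a high proportion of no appointment, ER visit, hospitalization), zero-inflated regression models will be employed". Repeated secondary outcomes otherwise follow the random-intercept approach used for A1C: "Number of logins and the repeatedly measured secondary outcomes will be analyzed with the same approach using the GLMM".

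The Synopsis (Outcome Variables) fixes the counting window: "ER visits, and hospitalizations during the previous 3 months". Section 4 has the study "collecting data from participants at baseline, 3 and 6 months", and section 7.1 rests on "using a feasible sample size of 30 participants". Section 4.2.2 places these counts under engagement with care, a secondary outcome.

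The plan does not state:
- a threshold for a high proportion of zeros, or a comparison with the zeros the count model predicts;
- which covariates enter the zero part, or whether the random intercept is kept;
- a fallback if the fit does not converge;
- which coefficient is the reported effect.

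**The concern.** Zero inflation means more zeros than the fitted count model can explain. The plan's trigger is instead the share of zeros. An uncommon event counted over 3 months gives mostly zeros under an ordinary Poisson model, so the trigger cannot separate a rare event from a group of people who can never have one.

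Once triggered, the zero-inflated model has two parts. Unless the zero part is constant over time, neither part alone gives the change in mean events, which is the natural reading of change over time in visits or admissions. The results for ER visits and hospitalizations could then be an effect measure that nobody chose in advance. If the model behaves badly, its replacement would be chosen after the data are seen.

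**Working it through.** **Inputs.** From the documents: 30 people, three time points, hence at most 30 x 3 = 90 person-periods, with a 3-month window. Assumed, because the documents give no event rates: a mean m of 0.1 to 0.5 events per window. The plan states no figure on this point to reproduce.

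**1. Zeros without inflation.** For a Poisson count, P(0) = exp(-m). For a negative binomial count with variance m + 2m², P(0) = (1 + 2m)^(-1/2).

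| m | Poisson zeros | Negative binomial zeros |
|---|---|---|
| 0.1 | 90% | 91% |
| 0.2 | 82% | 85% |
| 0.3 | 74% | 79% |
| 0.5 | 61% | 71% |

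None of these counts is zero-inflated. If a high proportion meant more than half (an assumption), every simulated trial with m of 0.5 or less met the trigger.

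**2. Information on the zero part.** Telling inflation from a low rate depends on person-periods with two or more events. At m = 0.1, 90 x 0.1 = 9 events are expected. P(two or more) = 1 - exp(-0.1) x (1 + 0.1) = 0.0047, and 90 x 0.0047 is about 0.4 person-periods.

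**3. Constant zero part.** The mean is (1 - p) x λ. The ratio between two times is (1 - p)λ₁ / (1 - p)λ₀ = λ₁/λ₀, so the count coefficient is still the log ratio of means.
- In 300 simulated trials per setting (30 x 3, no inflation, no between-person variation), 69%, 59% and 66% of zero-inflated Poisson fits at m = 0.1, 0.2 and 0.3 were flagged (p below 0.01 or above 0.99, non-convergence or non-finite errors).
- A repeat with several starting values had p below 0.01 in 70%, 59% and 62%, and above 0.99 in none. In those fits the time slope differed from the Poisson slope by a median below 0.000001; in the remaining fits, by 0.006 to 0.015 on the log scale.
- So most flagged fits are the Poisson model under another name. With gamma between-person variation (variance 1) at m = 0.2, 29% were flagged.

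**4. Time also in the zero part.** Suppose the never-at-risk share goes from 50% to 75% with λ = 1 throughout. The count-part ratio is 1.0, but the mean goes from 0.50 x 1 = 0.50 to 0.25 x 1 = 0.25, a ratio of 0.5.
- In simulation (true ratio 0.7 over 6 months, m from 0.2 to 0.5, gamma variance 0 or 1), the count slope differed from the Poisson mean slope by a median of 0.17 to 0.67 log units, with a robust standard deviation up to about 1.8 times larger.
- At m = 0.2 with variance 1, the 5th to 95th percentile range of the count-part ratio was 0.20 to 1.85 with a constant zero part and 0.10 to 4.80 with time in it.

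**5. Alternative.** A Poisson GEE with robust errors (m from 0.1 to 1.0) failed in 0 to 4% of trials, with median ratio 0.62 to 0.76 against the true 0.70. Coverage of the 95% interval was 92 to 95% at gamma variance 0 or 1, and 83 to 89% at variance 3.

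The zero-inflated fits in steps 3 and 4 left out the planned random intercept, which would add a further parameter.

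**The case against.** A reader might infer that zero-inflated models will usually break down with 30 people, or that they necessarily estimate the wrong quantity. Neither follows.
- **Breakdown.** Most boundary fits are a harmless return to Poisson with the same slope; the practical nuisance is that standard errors may not print. The boundary share also falls with between-person variation, which is plausible here. With gamma variance 1, degenerate zero-inflated Poisson fits were 9 to 20% at m = 0.5 and 1 to 6% at m = 1.0 (wider definition: also standard errors above 5 or extreme coefficients; constant and time-dependent zero part respectively).
- **Wrong quantity.** With a constant zero part the count coefficient is the log mean ratio, and the plan does not say that time enters the zero part. The quantity is unspecified rather than wrong.
- **Appointments.** Means of 0.1 to 0.3 do not represent clinic visits by established patients, so the collapse figures should not be carried over to them.

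These three objections stand, and they limit the point.

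It can also be said that the rule means excess zeros in the usual sense, loosely worded, and that section 7.2 has distributions examined first. This carries less weight: the parenthesis defines the condition as a high proportion of zeros, and looking at central tendency and dispersion is not a comparison with expected zeros.

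Finally, these are secondary outcomes in a single-arm pilot for which section 3.2 specifies no hypotheses. That also stands, and it sets the priority.

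**Conclusion.** The point holds in a limited form. The trigger does not detect zero inflation; that is exact arithmetic once a mean is assumed, with 61 to 90% zeros for Poisson means of 0.5 down to 0.1. With at most 90 person-periods the zero part is barely identified. It then either adds nothing (constant zero part) or, if time enters it, gives a noisier count coefficient that is not the change in mean events.

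The 59 to 69% of flagged fits should be read as mostly collapse to Poisson, for rare counts without between-person variation. They are not a rate of unusable analyses. All simulated sizes rest on assumed event rates. The improvement is worth making but optional.

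**What to change.** Replace the zero-proportion trigger in section 7.2 with the following:
- Fit one log-link Poisson or negative binomial model for the mean count at 0, 3 and 6 months, with a person random intercept or as a GEE with small-sample robust errors. The coverage of 83 to 89% under strong between-person variation is the reason for the small-sample correction.
- Report the ratio of mean counts, with its interval, as the effect.
- Use a zero-inflated model only as a sensitivity analysis, when observed zeros exceed those expected under the fitted count model, and then report the marginal mean ratio.
- For outcomes with very few events, report the counts and the share of participants with at least one event at each wave.

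The cost is a few sentences of plan text and a simpler analysis. What is given up is a separate estimate of a never-user class, for which 30 people give little information.

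### Section 7.2 keeps an uncorrected partial eta squared, from at most 30 people and without an interval, as the per-factor effect size for future research; it is too large on average

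*Combined protocol and SAP*

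**What the plan says.** After the main mixed-model analyses, section 7.2 adds a supplementary regression: "We will also estimate the effects of portal use (frequency, type) and feasibility factors (e.g., acceptability, attendance, fidelity) on A1c at 6 months", with baseline A1C as covariate. It then says that, for later and larger research, "we will obtain an effect size (partial eta square) of each factor from GLM". Section 7.1 describes the whole of Phase 2 in similar terms: "Since this is a pilot study to provide preliminary data for a future large study". Section 5.2 sets enrolment at 30, 15 per clinic, so 30 is the ceiling for this model, and anyone without a 6-month A1C lowers it.

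Five factors are named (frequency and type of portal use, acceptability, attendance, fidelity), and the list is left open. The plan does not say how the factors are coded or whether they enter one at a time or together. It names no bias-adjusted index, no confidence interval for the per-factor values and no cut-off for calling a factor relevant.

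The primary Phase 2 objective in section 3.3 is a different quantity, the effect size of MAP on logins and on A1C. For A1C, section 7.2 plans a separate index: "We will estimate the Cohen's D effect size of MAP on A1C".

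**The concern.** Partial eta squared is the factor's sum of squares divided by that sum plus the error sum of squares. It cannot be negative, and it makes no allowance for the variation that a useless regressor picks up by chance. With a few hundred people this hardly matters. With 20 to 27 error degrees of freedom, the chance component is as large as the effects one would hope to detect.

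Calling the analysis exploratory does not settle the matter, because the plan says that these numbers are kept for a larger study. A later team that reads them at face value would see effects that are too large on average and, with no interval beside them, could not see how uncertain they are.

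**Working it through.** The plan states no figure for partial eta squared, so there is none to reproduce. The margin of ±0.27 in section 7.1 concerns the A1C change and does not enter here.

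**Inputs from the documents.** N is at most 30 (5.2); baseline A1C is the covariate and at least five factors are named (7.2).

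**Assumptions.** Each factor takes 1 df. Either one factor or five factors are in the model. A drop to 24 completers is shown as a sensitivity case. The true value of 0.05 is illustrative. The future study uses a 5% F test with 80% power.

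**Step 1: error df.** With an intercept, baseline A1C and m factors, v = N − 2 − m. This gives 30 − 2 − 1 = 27, 30 − 2 − 5 = 23, and 24 − 2 − 5 = 17.

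**Step 2: a factor with no effect.** Partial eta squared = F/(F + v). With no effect it follows Beta(1/2, v/2), whose mean is 1/(1 + v).

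| Case | v | Mean | Median |
|---|---|---|---|
| N=30, one factor | 27 | 1/28 = 0.036 | 0.017 |
| N=30, five factors | 23 | 1/24 = 0.042 | 0.020 |
| N=24, five factors | 17 | 1/18 = 0.056 | 0.027 |

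A factor with 3 df, which portal-use type could be, averages 3/28 = 0.107 at N=30 when it is the only factor beside baseline A1C.

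**Step 3: a true value of 0.05, N=30.** Simulation with normal data and random regressors, 40,000 runs per case:

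| Quantity | One factor | Five factors |
|---|---|---|
| Mean partial eta squared | 0.081 | 0.086 |
| Median | 0.053 | 0.055 |
| Share of runs above 0.05 | 52% | 52% |
| SD of the estimate | 0.084 | 0.092 |
| Central 95% of estimates | 0.00 to 0.30 | 0.00 to 0.33 |

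The bias is 0.081 − 0.05 = 0.031 and 0.086 − 0.05 = 0.036. The SD is roughly two and a half times that. If the regressors are treated as fixed (noncentrality 30 × 0.05/0.95 = 1.58), the means are 0.084 and 0.097, so the result does not depend on that choice.

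**Step 4: consequence if such a mean were used for planning.** Let f² = η²/(1 − η²) and noncentrality = f² × N, with one factor plus baseline A1C.

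- η² = 0.05: f² = 0.0526, N = 152.
- η² = 0.08: f² = 0.0870, N = 93.
- η² = 0.09: f² = 0.0989, N = 82.

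If the truth is 0.05, N = 93 gives noncentrality 93 × 0.0526 = 4.9 and power 59%. N = 82 gives 4.3 and power 54%.

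**Step 5: the adjusted indices.** For 1 df, partial epsilon squared = (F − 1)/(F + v) and partial omega squared = (F − 1)/(F − 1 + N). Without truncation at zero, both average about 0.000 for a factor with no effect. At a true 0.05 in the Step 3 simulation, epsilon squared averages 0.0469 (one factor) and 0.0465 (five), and omega squared 0.044 and 0.039. The SD of epsilon squared is 0.087 and 0.096, so the adjustment removes most of the bias and none of the imprecision.

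**The case against.** The strongest reply is that this is one supplementary sentence in a pilot which, by section 3.2, has no specified hypotheses. The effect sizes that define Phase 2 are those of MAP on A1C and logins, and Cohen's d at 29 df has only a small bias (correction factor 0.974). That stands, and it limits the weight of the point.

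A reader might go further and infer three things that the documents do not support.

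- *The next study will be undersized.* The plan keeps the values for future research but does not say that a sample size will be computed from them, and nothing says that a later MAP trial would be powered on portal-use or process factors. Even on that supposition, a single estimate exceeds a true 0.05 in only about 52% of runs, so oversizing is nearly as likely.
- *Factors with no effect will look relevant.* The plan sets no cut-off and plans no selection of factors. With an illustrative cut-off of 0.06, a factor with no effect exceeds it 20% of the time (v = 27) or 24% (v = 23), and the typical null value is about 0.02. That is a raised risk, not the expected outcome.
- *Supplying these per-factor values is the purpose of the pilot.* Section 3.3 puts the purpose elsewhere.

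Two stricter remedies also fail. Fitting each factor in its own model saves error df but changes the quantity estimated, from an effect adjusted for the other factors to one that is not; that is a trade-off for the sponsor. Planning from the interval alone is impractical: at a true 0.05 the F test is significant in only about 19% to 22% of runs, so the interval would usually reach zero and give no finite sample size at that end.

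None of this answers the core: the index is biased upward on average, no interval accompanies it, and an index with much less bias comes from the same fit.

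**Conclusion.** The point holds as a matter of which index is reported and with what statement of uncertainty. For a true 0.05, the average reported value is some 60% to 70% too high (0.031/0.05 to 0.036/0.05), while the median is close to right and sampling error dominates. The undersizing in Step 4 is conditional on a use that the plan permits but does not promise.

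The figures rest on 1-df factors, one to five of them in the model, normal data and an assumed true value. More factors, multi-df coding or missing 6-month A1C would make the bias larger. The direction of the bias depends on none of these choices. It is worth correcting because the correction is cheap, and it does not touch the primary analyses.

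**What to change.** In section 7.2, replace partial eta squared with partial epsilon squared or partial omega squared, not truncated at zero, and give a confidence interval for each factor. Add that the per-factor point values are descriptive and will not alone size the next study.

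This is a change of one or two sentences. It uses the F statistics and degrees of freedom of the model already planned and needs no new data. The price is in presentation: the reported values become smaller, and some will fall near or below zero (about 40% to 43% of runs for epsilon squared at a true 0.05). The intervals will be wide, which is an accurate picture of what 30 people can say about individual factors.
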